#### 12.2 Reproduction Risks:

All participants of child-bearing potential who are sexually active must agree to use two forms of birth control during their time in the study. Participants of childbearing potential will have urine pregnancy monthly, during a study visit or medication pick-up. Participants of childbearing potential who are sexually active will be instructed to use a highly effective birth control method. Participants of childbearing potential who think that they may be pregnant will be asked to stop taking the study medication and call the study doctor as soon as possible.

#### 12.3 Risks to Others:

Not applicable.

#### 12.4 Definition of Adverse Events (AE):

An adverse event is any untoward medical occurrence in a clinical trial subject that is temporally associated with the use of the medicinal product, whether or not considered related to the medicinal product. An adverse event can be any unfavorable and unintended sign, including an abnormal laboratory finding, symptom or disease (new or exacerbated) temporally associated with the use of a medical product.

#### 12.5 Definition of Serious Adverse Events (SAE):

A SAE is an AE that fulfills at least one of the following criteria:

- Results in death
- Is life-threatening
- Requires inpatient hospitalization or prolongation of existing hospitalization
- Results in persistent disability/incapacity
- Is a congenital anomaly/birth defect

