Patient Health Questionnaire-9 (PHQ-9): The PHQ-9 measures depression and suicidality. The PHQ-9 Modified for Teens will be administered to participants < 18 years of age. A participant will be referred to a mental health professional or primary care provider if s/he has a PHQ-9 score of  $\geq 10$  or reports any suicidal behavior. A PHQ-9 score  $\geq 15$  at the screening vision is an exclusion criteria.

Columbia-Suicide Severity Rating Scale (C-SSRS): The C-SSRS measures depression and suicidality. A participant will be referred to a mental health professional or primary care provider if s/he has any suicidal behavior or any suicidal ideation of type 4 or 5 on the C-SSRS. Please see Exclusion Criteria for cut-off scores related to the C-SSRS.

Pediatric Quality of Life Inventory (PedsQL™): The PedsQL measures general and disease-specific quality of life. We will be using the participant-reported measures for the PedsQL™ Generic Core Scales and Diabetes Module Version 3.2 for young adults (aged 18-25 years) and Teens (12-18 years).

Oral Glucose Tolerance Test (OGTT): Insulin sensitivity and  $\beta$ -cell function will be measured via a 2-hour, 75 mg oral glucose tolerance test. OGTT has been widely used in the evaluation of  $\beta$ -cell dysfunction and T2D, including in the TODAY and RISE studies. The OGTT will be performed following a 10-12 hour overnight fast. Participants will take their last dose of metformin (if applicable) the evening before testing. Participants on basal or bolus insulin will be asked to withhold insulin dose either 36 hours or 6 hours, respectively, prior to testing. Plasma glucose levels, C-peptide, and insulin levels will be measured at baseline, 30, 60, 90 and 120 minutes following standard glucose ingestion. If a participant comes to a visit and has not withheld insulin for the required number of hours, the visit

will proceed without the OGTT and the participant will be asked to return to perform the OGTT within one week of the originally scheduled visit.

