## **12.0 Risks to Participants**

### *12.1 Foreseeable Risks:*

#### *Expected Adverse Events*

PHN/TPM: Adverse events will be reviewed and documented at each study visit and phone call (monitored monthly throughout the study). Participants will be instructed to contact study staff immediately if any adverse event is experienced. Overall, the safety profile of PHN/TPM has been demonstrated to be acceptable in adults, with paresthesia (mild tingling in the extremities), dysgeusia (altered taste), insomnia, constipation, and dry mouth as the most commonly reported (incidence  $\geq 5\%$ ). Of note, topiramate use during the first trimester of pregnancy is associated with an increased risk of oral clefts in the fetus. A basic metabolic panel at weeks 0, 24, and 52, and urine pregnancy test (for persons of child-

bearing potential) will be performed monthly. We will require all sexually active participants who are of child-bearing potential to confirm use of at least two forms of effective contraception. In addition, we will monitor for potential changes in depression, anxiety, suicidal behavior and ideation, acute myopia and secondary angle closure glaucoma, mood and sleep disorders, cognitive impairment, metabolic acidosis, kidney stones, and elevated creatinine. Participants will be asked to increase their fluid intake in order to help decrease the concentration of substances involved in kidney formation. Topiramate can increase the risk of suicidal ideation and behavior. Participants will be screened for depression with the PHQ-9 and suicidal ideation and behavior with the C-SSRS. If any questionnaire reveals suicidal behavior or ideation with some intent to act on it, then test results will be confirmed by the PI prior to discharging the subject from the study. Study medications will be weaned off if there is suicidal behavior or ideation with some intent to act on it.

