#### 12.6 Classification of an Adverse Event

Severity of Event. The severity of all AEs will be assessed by the study clinician using the following grading system:

- Grade 1: Mild. Asymptomatic or mild symptoms, clinical or diagnostic observations only, intervention not indicated.
- Grade 2: Moderate. Minimal, local or noninvasive intervention indicated, limiting age-appropriate instrumental activities of daily living.
- Grade 3: Severe. Medically significant but not immediately life-threatening, hospitalization or prolongation of hospitalization indicated, disabling, limiting self-care activities of daily life.
- Grade 4: Life-threatening. Urgent intervention indicated.
- Grade 5: Death related to adverse event.

Relationship to Study Intervention. All AEs must have their relationship to study intervention assessed by the clinician who examines and evaluates the participant based on temporal relationship and his/her clinical judgment. The degree of certainty about causality will be graded using the categories below. In a clinical trial, the study product must always be suspect.

- Unrelated: clearly not related to the investigational agent(s)
- Unlikely: doubtfully related to the investigational agent(s)
- Possible: may be related to the investigational agent(s)
- Probable: likely related to the investigational agent(s)
- Definite: clearly related to the investigational agent(s)

Expectedness: The study clinician will be responsible for determining whether an AE is expected or unexpected. An AE will be considered unexpected if the nature, severity, or frequency of the event is not consistent with the risk information previously described for the study intervention.

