**Participant Safety:** At the outset, participant risk will be minimized by study team adherence to exclusion and inclusion criteria during screening. The proposed research will expose the participants to a minor increase over minimal risk. The exclusion criteria include, but are not limited to, contraindications to PHN/TPM. Participant assessments will be done at study visits every three months. Participants and their parent/guardian (if < 18 years) will be provided with contact information for [name] (study PI), clinical nurse, and the research coordinator with explicit instructions to contact the study team in the event of emergencies.

**Participant Stopping Rules:** In the event that a participant has a serious adverse event that is deemed related to the study medication and/or procedures by the PI, the participant will be required to immediately discontinue the intervention. The overall study may be stopped at any time at the request of the PI and/or the DSMB. Participants will be removed from the study if suicidal ideation, excessive

weight loss, or disordered eating is present at any time during the trial or if any clinically significant changes (at the discretion of the PI) in mood and/or depression are observed. If the ratio of participants on medication vs. placebo developing a serious adverse event requiring withdrawal exceeds 4:1 (after  $\geq 50\%$  enrollment and a minimum of 5 total events, regardless of group assignment), the trial will be stopped. Patients will be instructed that they may withdraw from the study at any time and for any reason without impact on their typical clinical care.

**Study Integrity:** As stated above, the study will undergo annual monitoring of the facility, staff, and study documents by clinical research associates of the University of Minnesota Clinical Trials Monitoring Service. Monitoring staff will provide a summary report to [name] and her mentorship team after each site visit. If necessary, corrective action plans will be devised and implemented by [name] to address deficiencies.

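### The SAE definition in section 12.5 has no important-medical-event criterion, so removals that the protocol itself orders can go uncounted by the 4:1 stopping rule

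*Combined protocol and SAP*

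**What the plan says.** Section 12.5 opens with "A SAE is an AE that fulfills at least one of the following criteria" and gives five: death, threat to life, an event that "Requires inpatient hospitalization or prolongation of existing hospitalization", persistent disability or incapacity, and congenital anomaly or birth defect. The list ends there, with no item that rests on the investigator's judgment of medical importance. Section 12.6 does use the words "Medically significant but not immediately life-threatening", but as part of severity Grade 3, which is not linked to seriousness.

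Elsewhere the protocol acts on events without asking whether they are serious:

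- Section 12.1: "Study medications will be weaned off if there is suicidal behavior or ideation with some intent to act on it".
- Section 17.2, participant stopping rules: "Participants will be removed from the study if suicidal ideation, excessive" and, continuing, "weight loss, or disordered eating is present at any time during the trial or if any clinically significant changes (at the discretion of the PI", the changes in question being in mood or depression.
- Section 5.2, on the C-SSRS: "A participant will be referred to a mental health professional or primary care provider if s/he has any suicidal behavior", or ideation of type 4 or 5.

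The study-level rule, also in section 17.2, stops the trial if the ratio of drug to placebo participants with a "serious adverse event requiring withdrawal exceeds 4:1". It applies once at least half the sample is enrolled and at least five events have occurred in total.

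**The concern.** The events that the protocol treats as grave enough to end drug or participation are not the events that its numerical stopping rule counts. The two sets overlap only where a removal event also happens to be life-threatening, disabling or admitted, or meets another section 12.5 criterion. Topiramate's suicidality risk is named in section 12.1, and the route laid down for a positive screen is referral. A participant could therefore leave the trial for one of the risks it watches most closely without adding to the count that is meant to stop it.

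At stake is the sensitivity of the one prespecified, comparative safety rule in a blinded trial of 30 adolescents. Some reporting and late recording duties also depend on SAE status.

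**Working it through.** The plan gives no figure to reproduce here. The check sets the sections side by side and then applies the stopping rule as written.

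**Step 1. Which protocol-ordered removals are SAEs?**

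| Event | Action in the protocol | Does the action require admission? | SAE under 12.5? |
|---|---|---|---|
| Suicidal behavior, or ideation with intent | Drug weaned off (12.1); referral (5.2) | No | Only if one of the five criteria is also met |
| Suicidal ideation | Removal (17.2) | No | Same |
| Excessive weight loss | Removal (17.2) | No | Same |
| Disordered eating | Removal (17.2) | No | Same |
| Clinically significant mood change | Removal at the PI's discretion (17.2) | No | Same |

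Each event can end drug or participation and still be a non-serious AE.

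**Step 2. When does the 4:1 rule fire?** Let *a* and *b* be the drug and placebo participants with an SAE requiring withdrawal. With at least 50% enrolled (15 of 30), the rule needs *a* + *b* ≥ 5 and *a* > 4*b*. I take *b* = 0 with *a* ≥ 5 as exceeding 4:1.

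- 5 events: 5:0 fires (5 > 0). 4:1 does not (4 is not above 4).
- 6 events: 5:1 fires (5 > 4).
- 7 events: 6:1 fires (6 > 4).

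One uncounted drug-arm event is enough to change the result at these margins. 5:0 becomes 4:0, which is below five events, and 5:1 becomes 4:1, which is not above the ratio.

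**Step 3. Hypothetical case.** At least half the sample is enrolled. Five drug-arm and no placebo participants are removed for events that meet none of the five criteria.

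- Section 12.5 as written: 0:0, total 0 < 5, so the rule cannot fire.
- All five judged serious: 5:0, total 5 ≥ 5 and 5 > 0, so the rule fires.

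**Step 4. Illustration over assumed rates.** The documents give no rate for these events. Assume 15 per arm (section 14.2), a 2% placebo rate, and a share *q* of events classed as SAEs in both arms. For one look at the final totals, the probability of firing is the sum of Bin(*a*; 15, *q*·p_drug) × Bin(*b*; 15, *q*·0.02) over all *a*, *b* with *a* + *b* ≥ 5 and *a* > 4*b*.

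| Assumed drug-arm rate | All count | Half count | None count |
|---|---|---|---|
| 10% | 0.012 | 0.001 | 0 |
| 20% | 0.158 | 0.013 | 0 |
| 30% | 0.468 | 0.061 | 0 |
| 40% | 0.758 | 0.163 | 0 |

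**Step 5. Other consequences of non-serious status (section 12.7).**

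- *Recording.* The 7 and 30 days limit the start dates of events to be recorded after the last day of participation. An event that causes removal starts on study and is recorded either way. What is lost is a non-serious event that starts on days 8 to 30.
- *Reporting.* The event falls outside the SAE-based IRB and FDA reports. IRB notification also requires the event to be unexpected, at least possibly related, and to increase risk. One FDA sentence, on SAEs that are not fatal or life-threatening, gives 15 days without requiring unexpectedness.

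**The case against.** The strongest reply is that these events are well watched without SAE status, and on the text this is largely right. Removal, weaning and referral (sections 17.2, 12.1, 5.2) do not depend on seriousness. Section 12.7 records all AEs, follows them to resolution, and sends AE as well as SAE data to the DSMB no less often than every six months. Under section 17.2, AEs are reviewed after each study visit, the statistician is to raise any disproportion between groups, and the PI or DSMB may stop the study whenever they choose. A reader might infer that every safety action hangs on the word serious, or that these events escape oversight. The documents do not support either reading.

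Three other stronger readings also fail:

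- That such an event is an SAE only on admission. The life-threatening and disability criteria need no admission, and Grade 3 in section 12.6 itself mentions indicated hospitalization and disability, so it is not a grade for outpatient events.
- That 30-day follow-up is lost. The window governs start dates only.
- That section 12.5 departs from the federal regulation cited in section 12.7. The documents do not reproduce its definition of serious, so this cannot be judged from them.

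It is also fair to say that the hypothetical case is extreme. It puts 5 of 15 drug participants (one third) in this category. Section 8.2 excludes recent ideation and past attempts, and the 55-patient chart review in section 2.2 lists no suicidality among its most common events. Expedited reporting would not always follow from SAE status either, since section 12.1 already describes suicidality as a risk.

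What stands after all this is the stopping rule. The backstops are periodic or discretionary, and none of them adds an uncounted removal to the prespecified ratio.

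**Conclusion.** The point holds in a limited form. Section 12.5 is a closed list without an important-medical-event criterion, so removals ordered by sections 12.1 and 17.2 may be non-serious AEs and may go uncounted by the only numerical study-level stopping rule. This is a stated rule that can give a weaker safety result when followed as written.

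The size is definite in the hypothetical case (0:0 against 5:0) and otherwise unknown. Over assumed drug-arm rates of 20% to 40%, the chance that the rule fires falls from 0.158–0.758 if all such events count to 0.013–0.163 if half do, and to 0 if none do. At 10% it is 0.012 even when all count, so at low rates little is lost. These figures rest on the assumed 2% placebo rate, 15 per arm, one final look, and treating stopping drug or removal for such an event as withdrawal under the rule. The effects on reporting and late recording are real but narrower. I class this as a cheap improvement.

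**What to change.** Add a sixth criterion to section 12.5 for an important medical event in the investigator's judgment. State in sections 12.5 and 17.2 whether removals or drug stops under 12.1 and 17.2 are assessed against it, and whether those judged serious count toward the 4:1 rule. Leave the ratio, the five-event minimum and the enrollment condition as they are. Assessment does not make every such removal an SAE.

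One reconciliation has to come with it. Section 17.2 requires a participant with a related SAE to stop the intervention at once, while section 12.1 has drug weaned off for suicidal behavior or ideation with intent. Both already apply to an event of that kind that is serious and related, and more events would fall under both once the criterion is added. The passages must be reconciled. Which events qualify and how drug is stopped are for the sponsor and the DSMB to decide.

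The cost is one criterion, a clarifying statement, the reconciliation of two passages and an edit to the SAE form. The downside is a few more SAE assessments and possibly some expedited reports.

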#### 12.6 Classification of an Adverse Event

Severity of Event. The severity of all AEs will be assessed by the study clinician using the following grading system:

- Grade 1: Mild. Asymptomatic or mild symptoms, clinical or diagnostic observations only, intervention not indicated.
- Grade 2: Moderate. Minimal, local or noninvasive intervention indicated, limiting age-appropriate instrumental activities of daily living.
- Grade 3: Severe. Medically significant but not immediately life-threatening, hospitalization or prolongation of hospitalization indicated, disabling, limiting self-care activities of daily life.
- Grade 4: Life-threatening. Urgent intervention indicated.
- Grade 5: Death related to adverse event.

Relationship to Study Intervention. All AEs must have their relationship to study intervention assessed by the clinician who examines and evaluates the participant based on temporal relationship and his/her clinical judgment. The degree of certainty about causality will be graded using the categories below. In a clinical trial, the study product must always be suspect.

- Unrelated: clearly not related to the investigational agent(s)
- Unlikely: doubtfully related to the investigational agent(s)
- Possible: may be related to the investigational agent(s)
- Probable: likely related to the investigational agent(s)
- Definite: clearly related to the investigational agent(s)

Expectedness: The study clinician will be responsible for determining whether an AE is expected or unexpected. An AE will be considered unexpected if the nature, severity, or frequency of the event is not consistent with the risk information previously described for the study intervention.

#### 12.7 Time Period and Frequency for Event Assessment and Follow-Up

All AEs will be captured on the appropriate case report form (CRF). Information to be collected includes event description, time of onset, clinician's assessment of severity, relationship to study product (assessed only by those with the training and authority to make a diagnosis), and time of resolution/stabilization of the event. All AEs occurring while on study must be documented appropriately regardless of relationship. All AEs will be followed to adequate resolution.

Any medical condition that is present at the time that the participant is screened will be considered as baseline and not reported as an AE. However, if the study participant's condition deteriorates at any time during the study, it will be recorded as an AE.

The study staff will record all reportable events with start dates occurring any time after informed consent is obtained until 7 days (for non-serious AEs) and 30 days (for SAEs) after the last day of study participation. At each in person study visit the study staff will inquire about the occurrence of AEs/SAEs since the last visit. Events will be followed for outcome information until resolution or stabilization.

The PI will notify the IRB of any SAE that meets the definition of being unexpected (in terms of nature, severity or frequency), that is related or possibly related to participation in the research and places the subject or others at increased risk of harm per current IRB policy within five days of knowledge of the event. The PI will be responsible for notifying the FDA of any unexpected fatal or life-threatening suspected SAE as soon as possible, but in no case later than seven calendar days after the PI's initial receipt of the information in compliance with the FDCA (21 U.S.C. §§ 301 et. seq.) as well as the implementing regulations [Title 21 of the Code of Federal Regulations (CFR)]. Non-fatal or non-life-threatening SAEs will be reported to the FDA no later than 15 days after the PI's initial receipt of the information. The PI will report any (1) serious, unexpected suspected adverse reactions, (2) findings from other clinical, animal, or in-vitro studies that suggest significant human risk, and (3) a clinically important increase in the rate of a serious suspected adverse reaction to the FDA no later than 15 calendar days after determining that the information qualifies for reporting [21 CFR 312.32(c)(1)]. The PI will also submit annual progress reports within 60 days of the anniversary of the date that the IND becomes active.

The DSMB will be provided with AE and SAE information prior to their review of the study, at least every six months.

## **13.0 Potential Benefits to Participants**

### *13.1* Potential Benefits:

The interventions and outcome measures in the proposed study, with the exception of PHN/TPM, presents experiences to participants that are reasonably commensurate with those inherent in their actual or expected medical situations and typical clinical care. Since data from clinical trials in adults and adolescents with obesity have demonstrated reduction in BMI with PHN/TPM treatment, it is anticipated that PHN/TPM will provide greater BMI reduction and therefore improved insulin sensitivity and glycemic control than standard T2D care.

## 14.0 Statistical Considerations

### 14.1 Data Analysis Plan:

There are 3 analysis populations planned, Intention-to-treat (ITT) will include any participant randomized according to their treatment assignment. Per-protocol (PP) will include those without protocol violations and who were compliant ( $\geq 80\%$ ) with their treatment assignment measured by medication log and medication collection. The safety population will include all who receive treatment, according to treatment received.

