**Table 2. Adverse Events of Phentermine/Topiramate Treatment in Adolescents with Obesity**

Adverse Event Description	Placebo Group (%)	Phentermine/Topiramate Group (%)
Dry Mouth	0%	8%
Abdominal Pain	0%	0%
Constipation	0%	0%
Diarrhea	0%	0%
Ear Infection	0%	0%
Nasopharyngitis	7%	0%
Pharyngitis	0%	0%
Procedural Pain	7.1%	0%
Urine Osmolarity Increase	0%	0%
Back Pain	0%	0%
Headache	21%	15%
Paresthesia	7%	31%
Dizziness	7%	0%
Insomnia	7%	0%
Oropharyngeal Pain	7%	0%

At 56 days, the percent change in body weight was +1.1±2.8% in the placebo group and -5.0±3.4% in the PHN/TPM group (placebo-subtracted weight loss of 6.1%). Owing to the relatively small sample size and the fact that weight reduction was a secondary outcome variable, the manufacturer did not perform a statistical analysis on these results. However, the preliminary results further support our estimated treatment effect, particularly considering the treatment period was only two months (56 days). Indeed, the degree of placebo-subtracted

weight loss was slightly better than what was observed in the adult trials at the two-month time-point, suggesting that the effects are at least additive when these two medications are used together.

In summary, this portfolio of preliminary work: 1) demonstrates our Center's leadership role in, and commitment to, the field of pediatric obesity medicine; 2) highlights the benefits (weight loss and cardiometabolic risk factor improvement) as well as our experience with this intervention; 3) provides preliminary evidence supporting the safety, efficacy, and acceptability of combination therapy in adolescents with severe obesity; and 4) sets the stage for taking this next important step.

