When an individual participant transitions from the placebo-controlled portion of the study to the open-label portion of the study, the study physician will put in orders for the open label study for IDS to dispense medication and the IDS staff will review the patient randomization and will either continue to fill the prescription with the maintenance dose or fill the prescription to have the participant titrate up on the study medication in order to help keep the study team blinded.

4.3 Biosafety:  
Not applicable.

4.4 Stem Cells:  
Not applicable.

4.5 Fetal Tissue:  
Not applicable

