## 5.0 Procedures Involved

### 5.1 Study Design:

This is a pilot, pragmatic, randomized trial with 6-month placebo-controlled period followed by a 6-month open label extension. Thirty pubertal or post-pubertal adolescents will be randomized into one of two arms:

- PHN/TPM
- Placebo

MEDICAL PROTOCOL PEDS-2021-29785

PROTOCOL TITLE: Phentermine/Topiramate in Adolescents with Type 2 Diabetes and Obesity

VERSION DATE: 10Dec2024

Participants will engage in typical T2D clinical care and lifestyle management, with the addition of PHN/TPM or placebo therapy for 6 months followed by a 6-month open label extension during which all participants will be given PHN/TPM in an unblinded fashion.

The schedule of events (below) shows the data that will be collected at each study visit.

MEDICAL PROTOCOL PEDS-2021-29785

PROTOCOL TITLE: Phentermine/Topiramate in Adolescents with Type 2 Diabetes and Obesity

VERSION DATE: 10Dec2024

Schedule of Events

Week	Screening	Baseline	Placebo-Controlled												
	-4%	0%	4	8	12%	16	20	24%	28	32	36%	40	44	48	52%
Informed consent/assent	X														
Demographics	X														
Medical and medication history	X														
Review of inclusion/exclusion criteria	X														
Randomization		X													
Urine pregnancy test d	X	X	X	X	X	X	X	X	X	X	X	X	X	X	X
Physical Exam	X	X			X			X			X				X
Tanner staging	X				X			X			X				X
Anthropometrics a	X	X	X	X	X	X	X	X	X	X	X	X	X	X	X
Vital signs (Blood pressure and heart rate)	X	X			X			X			X				X
EKG		X													
Contraceptive counseling	X	X	X	X	X	X	X	X	X	X	X	X	X	X	X
Adverse events			X	X	X	X	X	X	X	X	X	X	X	X	X
Hemoglobin A1c		X			X			X			X				X
Eating Disorder Examination Questionnaire (EDE-Q)		X			X			X			X				X
Peds-QOL (general and diabetes modules)		X						X							X
Patient Health Questionnaire (PHQ-9)	X				X			X			X				X
Columbia-Suicide Severity Rating Scale (C-SSRS)	X				X			X			X				X
Total daily insulin dose assessment		X			X			X			X				X
Oral Glucose Tolerance Test (OGTT)		X						X							X
ALT, AST, INR, TSH, bilirubin, albumin, basic metabolic panel	X							X							X
Lipid profile, vitamin D 1,25 b		X													
Plasma glucose level b		X						X							X
c-peptide level b		X						X							X
Insulin level b		X						X							X
iDXA (visceral and total body fat and bone mineral density)		X						X							X
Review of CGM data c			X	X	X	X	X	X	X	X	X	X	X	X	X

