### 14.3 Statistical Analysis:

Descriptive analyses of baseline characteristics and outcomes will include means and standard deviations, median and range for continuous variables and frequencies for categorical variables. Treatment adherence will also be evaluated by the methods described above. Safety analyses will be primarily descriptive reporting the number and percentage of adverse events. All safety outcomes will be evaluated and monitored throughout the trial. Confidence intervals (CIs) and p-values will be based on robust variance estimation. Statistical significance will be considered as  $p < 0.05$ .

Aim 1: The primary analysis will be conducted using the ITT population to compare the mean BMI percent change (primary outcome measure) from randomization to 6 months of follow-up between the groups, adjusted for BMI at randomization for added precision. We hypothesize that with participants treated with PHN/TPM will demonstrate greater BMI percent change compared to controls at 6 months. Supportive analyses using the PP population will also be conducted along with consideration of adjustment for residual imbalances

between treatment groups after randomization (e.g., in sex as a biological variable). Longitudinal analyses will also be conducted, incorporating the multiple time points through the open-label extension (6 months to 12 months follow-up) during which these BMI measurements will be obtained. This will examine durability of changes observed over the masked portion of follow-up, as well as provide additional safety information. Supportive analyses using the PP population will also be conducted.

Aim 2: Secondary outcomes will be analyzed in the same fashion as the primary endpoint wherein analyses will be adjusted for values at randomization. Outcome measures for Aim 2 are c-peptide index ( $\Delta C_{30}/\Delta G_{30}$ ), insulin sensitivity (1/fasting insulin),  $\beta$ -cell function relative to insulin sensitivity (oral disposition index [oDI]), A1c (%), and total daily insulin dose (units/kg/day). We hypothesize that participants treated with PHN/TPM will demonstrate improved insulin sensitivity and  $\beta$ -cell function compared to those assigned to placebo as measured by OGTT, A1c and total daily insulin doses. Complementary secondary analyses will also be conducted for each secondary outcome as described for the primary outcome.

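### The adverse-event summary and the 4:1 stopping ratio name no period and make no exposure adjustment, although every continuing participant takes PHN/TPM from week 24

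*Combined protocol and SAP*

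**What the plan says.** Section 14.1 defines the safety population: "The safety population will include all who receive treatment, according to treatment received". Section 14.3 describes the output: "Safety analyses will be primarily descriptive reporting the number and percentage of adverse events". It adds: "All safety outcomes will be evaluated and monitored throughout the trial". Neither section gives a cut-off week, a rule for participants who change treatment, or a denominator in time at risk.

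Section 5.1 describes the second half of the study as an "open label extension during which all participants will be given PHN/TPM in an unblinded fashion". Section 4.2 has the pharmacy, at that transition, either continue the maintenance dose or "fill the prescription to have the participant titrate up on the study medication". Placebo-arm participants who continue therefore start the drug at about week 24.

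Section 17.2 carries the stopping rule: "If the ratio of participants on medication vs. placebo developing a serious adverse event requiring withdrawal exceeds 4:1". It applies once at least half the participants are enrolled and at least five such events have occurred, and it names no period. The same section asks the statistician to flag events that occur disproportionately between the intervention groups, also without a period.

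By contrast, 14.3 limits the primary BMI comparison and the exploratory comparisons to randomization through 6 months. Section 12.7 requires onset time for each adverse event: "Information to be collected includes event description, time of onset".

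**The concern.** A randomized comparison with placebo exists only up to week 24. A rule based on treatment received gives one answer when each person receives one treatment. Here a placebo-arm completer receives two, and two groupings remain open.

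- **By starting arm over weeks 0-52.** Events caused by PHN/TPM in the extension are charged to placebo, which dilutes a true drug effect.
- **By treatment being taken at onset.** PHN/TPM gathers far more time at risk than placebo, so events unrelated to drug look more frequent on drug.

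The two err in opposite directions, and the plan leaves the choice to be made after the data are seen. The stopping ratio has the same gap. Counted by treatment at onset, it drifts toward stopping with no drug effect. Counted by original arm, open-label drug events enter the placebo count and make the rule less sensitive.

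**Working it through.** The plan states no figure for the adverse-event analysis, so there is none to reproduce.

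**Inputs.** 15 per arm (14.2); placebo-controlled period to week 24 and participation to week 52 (5.1, 5.3); 10% attrition (14.2); 36 months to enroll and complete everyone (5.3); paresthesia at 56 days, 31% of 13 on drug and 7% of 14 on placebo, from the table in section 2.2 titled "Adverse Events of Phentermine/Topiramate Treatment in Adolescents with Obesity". Assumptions are marked as such.

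**1. Exposure by treatment at onset.**
- PHN/TPM: 15×52 + 15×28 = 1,200 participant-weeks.
- Placebo: 15×24 = 360. Ratio 1,200/360 = 3.3.
- If 10% leave at week 12 (assumed timing): (13.5×52 + 1.5×12 + 13.5×28)/(13.5×24 + 1.5×12) = 1,098/342 = 3.2.

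**2. By treatment at onset, no drug effect.** Assume 7% per 8 weeks in everyone at constant risk, so the risk over w weeks is 1 − 0.93^(w/8).
- Placebo, 24 weeks: 1 − 0.93^3 = 0.196, or 2.9 of 15.
- PHN/TPM, 52 weeks: 1 − 0.93^6.5 = 0.376. PHN/TPM, 28 weeks: 1 − 0.93^3.5 = 0.224. Mean 0.300, or 9.0 of 30.
- True difference 0; apparent difference about 10 points (30% vs 20%).

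**3. By starting arm, weeks 0-52, true drug effect.** The result depends on when events start.

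| Assumption | Weeks 0-24, drug vs placebo | Weeks 0-52, drug vs placebo |
|---|---|---|
| Onset only at first exposure | 31% vs 7% (+24) | 31% vs 1 − 0.93×0.69 = 36% (−5) |
| Same, with 7% background also recurring on continued drug | 31% vs 7% (+24) | 1 − 0.69×0.93 = 36% vs 36% (0) |
| Constant risk, 31% or 7% per 8 weeks | 1 − 0.69^3 = 67% vs 1 − 0.93^3 = 20% (+48) | 1 − 0.69^6.5 = 91% vs 1 − 0.93^3×0.69^3.5 = 78% (+13) |

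The difference shrinks in every row. Its final sign does not follow from the design.

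**4. Stopping ratio by treatment at onset, no drug effect, given five qualifying events.** At five events, 4:1 does not exceed 4:1, so only 5:0 trips the rule. The probability is (drug share of exposure)^5.
- Trial end: (1,200/1,560)^5 = 0.27.
- Calendar week 52, assuming uniform enrollment over 104 weeks (36 months, about 156 weeks, less 52). Half are then enrolled, the earliest point at which the rule can act. Mean placebo time per placebo-arm participant is (24²/2 + 28×24)/52 = 18.5 weeks. Mean drug time is 26 weeks in the drug arm plus 26 − 18.5 = 7.5 weeks in the placebo arm. Ratio 33.5/18.5 = 1.8; probability (33.5/52)^5 = 0.11.
- Equal exposure: 0.5^5 = 0.03.

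**5. With a week-24 cut.** Each arm has 15×24 = 360 participant-weeks, and the illustrative paresthesia contrast stays at 31% vs 7%.

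**The case against.** The strongest reply is that this is a drafting gap in a 30-participant pilot with descriptive safety reporting. Section 14.1 only defines a population, and 14.3 does not say in terms that percentages will be compared by group. The design separates the two periods, 14.3 itself distinguishes the masked portion from the extension, and onset, severity and relatedness are recorded for every event. A competent analyst could split the periods unprompted, and no data are lost. A DSMB charter exists (17.2) and may define how events are counted.

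Much of that stands: the data support any split, and primary efficacy is untouched. But grouping by treatment received implies columns by treatment, and nothing requires the split. The masked-portion wording belongs to the longitudinal BMI analyses and sets no rule for adverse events. The charter is not in these documents and would not amend 14.1 or 14.3.

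A reader might infer three stronger claims that the documents do not support.
- **That the plan would probably reverse the paresthesia signal.** The −5 points rest on one onset assumption. Others give 0 or +13, and all use a 56-day study with 13 and 14 participants.
- **That the trial has a 27% chance of a false stop.** The 0.27 is conditional on five qualifying events and uses exposure reached only at trial end. If each of 30 participants had a 5% risk (assumed), five or more occur with probability about 1.6%, and 0.016×0.27 is about 0.4%. At 10% risk the figures are about 18% and 5%.
- **That the 14.3 percentages feed the checks in 17.2.** No text says so. The two places share the same omission.

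**Conclusion.** The point holds as an omission with consequences. Sections 14.1, 14.3 and 17.2 give no period, crossover rule or exposure basis for comparing adverse events, while the design puts every continuing participant on PHN/TPM from week 24.

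The exposure imbalance, up to 3.3:1 by treatment at onset, follows from the design with no dropout. The false excess of about 10 points assumes constant risk of 7% per 56 days. The 0.11 to 0.27 range assumes no drug effect, events in proportion to exposure, five qualifying events and, at its lower end, uniform enrollment over 104 weeks. The dilution under grouping by starting arm is clear in direction but has no single size.

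This should be corrected. It does not threaten the primary analysis.

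**What to change.** 1. In 14.1 and 14.3, make the comparative adverse-event table run from first dose to first open-label dose (weeks 0-24), by treatment received in that period.
2. Report the open-label period in a separate table by original arm, with participant-weeks and no placebo comparison.
3. In 17.2, apply the 4:1 ratio and the check for disproportionate events to weeks 0-24 events, or to events per participant-week.

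For item 3 the week-24 cut is the cleaner choice. If rates are used, the rule should also say what happens when placebo has no events, because five against none exceeds any ratio whatever the exposure.

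The cost is a few sentences and no new data, since 12.7 already records onset time. The downside is that harms first appearing after week 24 are seen only in an uncontrolled table. Under the week-24 cut the 4:1 rule would not act on them. They would still reach the DSMB, which under 17.2 can ask for the study to be stopped at any time.
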